11.3 Study Termination

Although CELLTRION, Inc. has every intention of completing the study, CELLTRION, Inc. reserves the right to discontinue the study at any time for clinical or administrative reasons.

Study termination is defined as the date on which the last subject completes the last visit (if the study is not discontinued by CELLTRION, Inc.).

11.4 Final Report

Whether the study is completed or prematurely terminated, the sponsor will ensure that the clinical study reports are prepared and provided to the regulatory agency(ies) as required by the applicable regulatory requirement(s). The sponsor will also ensure that the clinical study reports in marketing applications meet the standards of the ICH harmonised tripartite guideline E3: Structure and Content of Clinical Study Reports.

It is planned that 2 clinical study reports will be written.

13.2 Appendix 2: Flu-iiQ™

[Note: It is the Sponsor's responsibility to obtain copyright permissions for any scales or questionnaires]

1.1 Study Design and Plan

The Statistical Analysis Plan (SAP) is based on the final study protocol CT-P27 2.2 (A Phase IIb, Randomized, Double-blind, Multicenter, Placebo-controlled Study Evaluating the Efficacy and Safety of CT-P27 in Subjects with Acute Uncomplicated Influenza A Infection) Version 5.0 dated 31 January 2018 and electronic Case Report Form (eCRF) Version 4.1 dated 28 September 2017 and covers full study analysis and data presentation. This is a phase IIb, multicenter, placebo-controlled, randomized, double-blind, parallel-arm study to evaluate the efficacy and safety of two doses of CT-P27 (45 mg/kg and 90 mg/kg) in subjects with acute uncomplicated influenza A infection. This proof-of-concept study will provide dose-ranging information for the subsequent clinical development of the drug.

No study procedures will be performed prior to informing the subject about the study and obtaining written informed consent. However, any test result which was obtained within the allowed screening period can be used as screening data for subject's convenience. It is critical that subjects receive treatment with study drug no more than 48 hours after the onset of symptoms (window of +12 hours is allowed). The time of onset of illness is defined as the earlier of either (a) the time when the body temperature was first measured as $\geq 38.0^{\circ}\text{C}$ ($\geq 100.4^{\circ}\text{F}$) or (b) the time when the subject experienced the presence of at least two symptoms that are respiratory and/or constitutional (moderate to severe in intensity). For most subjects, obtainment of the Informed Consent Form (ICF), screening for eligibility, randomization and treatment will occur on the same day. Though obtainment of the ICF may occur on the day prior to screening, randomization or treatment, it must be within 24 hours before the administration of study drug.

To be eligible for enrollment, subjects must have a positive test result for influenza A by a rapid influenza diagnostic test. At screening, nasopharyngeal swab samples will be collected for two times to be used for rapid influenza diagnostic test and virology assessment. The enrollment process is presented in Figure 1.

Figure 1 Enrollment Process

[figure not shown]
Approximately 183 subjects with influenza A to be enrolled in the study will be randomly assigned to 1 of 3 groups, CT-P27 45 mg/kg, CT-P27 90 mg/kg, or placebo (approximately 70 subjects per CT-P27 treatment groups and 43 subjects in placebo group). Randomization will be stratified by flu vaccination history within a year (Yes vs No) and participation in Pharmacokinetic (PK) sub-study (Yes vs No). A schematic diagram of

CONFIDENTIAL

Statistical Analysis Plan

subject assignment is presented in Figure 2.

[figure not shown]
Figure 2 Schematic diagram of Subject Assignment

All enrolled subjects will be given a single dose of CT-P27 45 mg/kg, CT-P27 90 mg/kg, or placebo intravenously over 90 minutes (± 15 minutes) on Day 1 and then followed by Day 110.

A PK sub-study will be performed on the subjects who signed informed consent to participate in a PK sub-study. Of total number of subjects to be enrolled, approximately 53 subjects (20 subjects per CT-P27 treatment groups and 13 subjects in placebo group) will be included in the Subgroup (PK) Cohort, and additional PK samples from the subjects in this cohort will be collected according to the schedule of assessments. A schematic diagram for the study cohorts is presented in Figure 3.

Figure 3 Schematic Diagram for the Study Cohorts

Subjects may be admitted to a hospital from Day 1 (before study drug administration) to Day 3 (after completion of the 48 hours assessments) if deemed necessary by the investigator's judgement. The first analysis of data will occur after all subjects have completed the assessments scheduled for Day 15.

CONFIDENTIAL

Statistical Analysis Plan

As study recruitment was conducted through 2 influenza seasons to reach the expected sample size, approximately 1-year gap has been made between the subjects who enrolled during first season (randomized before 30Apr2017) and second season (randomized from 01May2017). To include as much available data as possible in the 1st Clinical Study Report (CSR), the whole data up to Day 110/EOS visit for the first season subjects, and the data up to Day 15 for the second season subjects will be summarized in the 1st CSR. In the Follow-Up CSR, the whole data up to study close will be included and summarized.

These data will be used to determine the efficacy of treatment with CT-P27 to establish an effect size of CT-P27 in comparison to placebo based on time to resolution of influenza symptoms and fever. Information on effect size, as well as the safety and PK will be used in the selection of doses for subsequent clinical studies.

2. Objectives

2.1 Primary Objective

To evaluate efficacy as determined according to the time to resolution of respiratory and constitutional symptoms of influenza and fever

2.2 Secondary Objectives

To evaluate the additional efficacy and safety of CT-P27, including potential effects on the incidence of Antibody-Dependent Enhancement (ADE)

2.3 Exploratory Objectives

- To assess the PK of CT-P27 components (CT-P22 and CT-P23)
- To assess immunogenicity
- To assess Hemagglutination Inhibition (HI) antibody
- To assess the characterization of isolated influenza viruses

3. Endpoints

3.1 Efficacy Endpoints

Primary Efficacy Endpoint:

The primary efficacy endpoint is defined as the time from the administration of study drug to resolution of influenza symptoms and fever as recorded in the diary.

Resolution of symptoms has occurred if the following influenza symptoms recorded on the Influenza Intensity and Impact Questionnaire (Flu-iiQ™) in the diary are mild in intensity or none for at least 24 hours.

- Respiratory symptoms (cough, sore throat, and nasal congestion)
- Constitutional symptoms (headache, feeling feverish, body aches and pains, and fatigue)

Resolution of fever is defined as:

- Body temperature of <37.0°C for at least 24 hours

Secondary Efficacy Endpoints:

- Time to resumption of normal activity as reported in Domain 2 of the Flu-iiQ™
- Time to return to normal body temperature (<37.0°C) for at least 24 hours
- Time to resolution of individual symptoms for at least 24 hours as reported in Domain 1 of the Flu-iiQ™
- Severity of symptoms as reported in Domain 1 of the Flu-iiQ™
- Viral shedding in nasopharyngeal swab samples
- Incidence of secondary complications of influenza
- Quality of Life (QoL) measures as reported in Domain 3 and Domain 4 of the Flu-iiQ™
- Physician assessment

Statistical Analysis Plan

3.2 Safety Endpoints

The following safety parameters are secondary endpoints:

- Treatment-emergent adverse events (TEAEs)
- Treatment-emergent serious adverse events (TESAEs)
- Clinical laboratory analyses (hematology, biochemistry, and urinalysis laboratory tests)
- Vital sign measurements
- Immediate hypersensitivity monitoring
- Electrocardiograms (ECGs)
- Physical examination findings
- Weight assessment
- Pregnancy test
- Chest X-ray
- Evaluation of ADE throughout the entire study duration

3.3 Exploratory Endpoints

- PK profiles:
 - $AUC_{0-\infty}$: Area under the concentration-time curve in serum from time zero extrapolated to infinite time
 - AUC_{0-last} : Area under the concentration-time curve from time zero to the last quantifiable concentration
 - C_{max} : Maximum observed serum concentration
 - t_{max} : Time of maximum concentration
 - C_{last} : Last observed quantifiable concentration
 - λ_z : Apparent terminal elimination rate constant
 - $t_{1/2}$: Apparent terminal elimination half-life
 - MRT : Mean residence time
 - CL : Systemic clearance from serum after IV dosing
 - V_z : Apparent volume of distribution during the terminal elimination phase after IV dosing
- Immunogenicity analysis:
 - Anti-drug specific antibodies and neutralizing antibodies for CT-P27 component antibodies (CT-P22 and CT-P23)
- HI antibody
- Genotype and phenotype of isolated influenza virus

4. Randomization, Stratification and Blinding

Subjects will be randomly assigned to a treatment group after they provide an ICF and meet all the inclusion criteria and none of the exclusion criteria by using Interactive Web Response System (IWRS). The randomization will be stratified by flu vaccination history within a year (Yes vs No) and participation in PK sub-study (Yes vs No).

This study will be double-blinded. The study blind will not be broken except in a medical emergency (where knowledge of the investigational medicinal product administered would affect the treatment of the emergency) or regulatory requirement (e.g., for Serious Adverse Event (SAE) or death). If the blind is broken, the date, time, and reason must be recorded in the subject's eCRF and any associated AE report.

The database will be unblinded to unblind person predefined by the sponsor [REDACTED]. However, the study will remain blinded to the investigators and subjects until study termination.

Statistical Analysis Plan

5. General Statistical Considerations

5.1 General Analysis Considerations

The statistical analysis will be performed using [REDACTED]. Any deviations from the planned analysis as described in this SAP will be justified and recorded in the CSR.

The data documented and the clinical parameters measured in this study will be described using descriptive statistics (including number [n], mean, median, Standard Deviation (SD), minimum, and maximum) for continuous variables: minimum and maximum will be presented to the same number of decimal places as the raw data, mean and median will be presented to one more decimal place than the raw data, and SD will be presented to two more decimal places than the raw data. If the geometric mean is to be presented, it will be set to the same precision as the mean. However, geometric mean will not be calculated when minimum value from the data is zero. Percent Coefficient of Variation (CV%) will be presented to two decimal places. P-values will be rounded to three decimal places. If a p-value is less than 0.001 it will be reported as "<0.001". If a p-value is greater than 0.999 it will be reported as ">0.999".

Categorical data will be summarized using count and percentage in each category. Percentages will be presented to one decimal place. The percentage will be suppressed when the count is zero in order to draw attention to the non-zero counts. "Not done" and "Missing" category will be included to account for cases of no assessment and missing respectively even if they are not recorded in eCRF. The denominator for all percentages will be the number of subjects within the treatment group for the population of interest, unless otherwise indicated.

All data will be displayed in listings. Unless otherwise specified, listings will be sorted by the treatment group, subject number, and assessment date or visit date, if applicable. In cases where more ordering is required, other variables will be included in the sort order as applicable.

Baseline will be the latest available measurement prior to the start of the infusion of study drug.

When summarizing End-of-Study (EOS) visit, the early termination cases are excluded from the summary for EOS visit, but will be presented in data listings. Unscheduled results will not be included in the summary tables except for determining baseline or if unscheduled results are necessary to interpret data, but they will be presented in data listings.

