 - Day 8: 168 hours (± 4 hours) after the start of the study drug infusion.
16. Sponsor-supplied or agreed in advance rapid influenza diagnostic test material will be used. And if there is available test result confirmed as influenza A prior to obtaining written informed consent and that result was from the influenza diagnostic test which is agreed with Sponsor in advance, that test result can be allowed. At screening, testing must be performed within 24 hours before study drug administration. Subjects with a negative test result by rapid diagnostic test, who have onset of symptoms within 48 hours (window of $+12$ hours is allowed) before study drug administration, can be rescreened only once.
17. The Investigator or designee will perform a symptom-directed physical examination (which should include, at a minimum, the examination of ear, nose, throat, sinuses, and lungs) and assessment for potential complications of influenza.
18. The subject will record the results of the Flu-iiQ™ in the diary.
- Flu-iiQ™ will be recorded once by the subject at the screening visit and will be recorded twice a day (at approximately 12-hour intervals) from Day 1 to Day 8 (in the morning [between 6 and 10 AM, approximately] and in the evening [between 6 and 10 PM, approximately]).
19. Body temperature which a subject experiences in prior to screening will be collected and body temperature taken with any type of thermometer will be acceptable. However, from the screening period, Sponsor-supplied thermometer will be used.
- Temperature will be measured by subject; It will be recorded twice a day (at approximately 12-hour intervals) from Day 1 to Day 8 (in the morning [between 6 and 10 AM, approximately] and in the evening [between 6 and 10 PM, approximately]).
 - Temperature will be measured by site personnel at site: at screening, Day 1 (prior to infusion), Day 2 (± 4 hours), Day 3 (± 4 hours), Day 5 (± 4 hours) and Day 8 (± 4 hours).
 - These will be used for assessment of endpoint.
20. Use of all medications, from 30 days prior to randomization and up until Day 110/EOS visit, will be recorded in the subject's eCRF.
21. AEs will be collected from the date the informed consent form is signed until Day 110/EOS visit.
22. EOS visit will be done at Day 110. But if a subject is early terminated from the study, EOS visit will be done to assess safety parameters at any time.

Schedule of Assessments (Unscheduled Visits Subjects with suspicious ADE)

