4.3.4 Subject Withdrawal

All subjects are free to withdraw from participation in the study at any time, for any reason, specified or unspecified, and without prejudice to further treatment. If a subject chooses to withdraw from the study, they will be encouraged to return to the site for safety reasons to complete the assessments planned for EOS visit

The Investigator will ensure that all reasonable attempts (telephone calls, contact with primary care physician, certified letter) are made to obtain follow-up safety information on subjects who do not return to the site for study visits or are lost to follow-up.

Subjects who are withdrawn from the study after randomization will not be replaced.

Subjects who withdraw from the study after dosing will be advised by the Investigator to continue contraception restrictions for 5 months after the administration of study drug.

The Investigator will ensure that the reasons for withdrawal are documented on the subject's medical records (source documents) and in the electronic Case Report Form (eCRF). If the subject withdraws due to an AE, the details of the AE must be entered on the AE section of the eCRF. If the reason for subject withdrawal is not known, the subject must be contacted and followed up in order to establish whether the reason for withdrawal was an AE, and if so, this must be reported in accordance with the procedures outlined in [Section 6.2.1.5](#).

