6.3 Exploratory Assessments

A PK sub-study will only be performed on the subjects who signed additional informed consent to participate in a PK sub-study. Blood sampling for PK analysis will be collected from subjects on Day 1 at pre-infusion (within 15 minutes prior to the beginning of the infusion), the end of infusion (within 15 minutes after the end of the infusion), 1 hour (± 15 minutes) after the end of the infusion, and then on Day 2 (24 hours [± 4 hours] after the start of the study drug infusion), Day 3 (48 hours [± 4 hours] after the start of the study drug infusion), Day 8 (168 hours [± 4 hours] after the start of the study drug infusion), Day 15 (± 2 days), Day 29 (± 5 days), Day 57 (± 5 days), and Day 110 (± 5 days)/EOS visit.

Samples taken on Day 1 will be collected in the opposite arm from that being used for the IV infusion of study drug. The date and time of collection of each sample and any missing blood draws will be recorded in the respective eCRF. Samples will be collected, labeled, stored, and shipped as detailed in the Laboratory Manual.

Bioanalysis will be carried out for the simultaneous determination of CT-P22 and CT-P23 using a validated ligand binding assay. Bioanalysis will be carried out at the bioanalytical site. Contact details for the bioanalytical site are available in Table 4.

Blood will be drawn at Day 1 (before study drug administration) and Day 110/EOS visit to evaluate the immunogenicity of CT-P27 components, CT-P22 and CT-P23. Samples will be secured at the central laboratory for immunogenicity analysis and backup samples will be retained.

For the subjects with Influenza A confirmed by qPCR or cell culture, genotypic analysis on HA and NA genes, and phenotype characterization of potential escape variants with regard to CT-P27 will be evaluated using the nasopharyngeal swab samples. Samples will be secured at the central laboratory for analysis and backup samples will be retained.

In addition, blood samples will be taken at Day 1 (at pre-infusion) and Day 29 (± 5 days)/EOS visit (if a subject is early terminated from the study) to determine HI antibody in Subgroup (PK) Cohort.

Primary samples will be secured at the central laboratory for PK, immunogenicity of CT-P22 and CT-P23, and HI antibody analysis and backup samples will be retained. Back-up samples will be retained up to 5 years after the end of the study unless a specific authorization is

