8.4.3 Safety Population

The safety population is defined as all randomized subjects receiving any amount of placebo or CT-P27. All safety and immunogenicity analyses will be based on the safety population.

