11.2 Immunogenicity Analysis

Immunogenicity will be assessed in the safety population by baseline and post-treatment serum measures of anti-CT-P27 component antibodies, CT-P22 and CT-P23 antibodies, using immunoassay. Immunogenicity assessments consist of both Anti-Drug Antibody (ADA) and Neutralizing Antibody (NAb) assays. The ADA

Statistical Analysis Plan

assay will follow a three-tiered approach consisting of (i) screening assay, (ii) specificity/confirmatory assay, and (iii) titration. The test outcome for the screening assay will be: {"Potential Positive" or "Negative"}. Samples that are "Potential Positive" in the screening assay will be undergone further testing in the specificity/confirmatory assay to determine if subjects are a true positive. The test outcome for the specificity/confirmatory assay will be: {"Reactive", "Negative", and "Not applicable (N/A)"}. "Reactive" indicates a true positive test outcome, "Negative" is considered negative and "N/A" indicates the assay was negative at the screening phase of the process. Subjects with a "Negative" test outcome for either screening or specificity/confirmatory assays will be considered negative for the overall ADA assessment. For further characterization, quantitative antibody level will be assessed by titration in confirmed positive samples. The ADA value of the CT-P22 and CT-P23 tagged assay will be transformed using a log transformation. Transformed ADA value can be obtained using $[\log_2(X/20)] + 1$ transformation.

Samples that are positive in the assessment will be analyzed further to conduct a NAb assessment. The same three-tiered approach of ADA assay will be applied to NAb assay. Transformed NAb value can be obtained using $[\log_2(X/10)] + 1$ transformation. If ADA or NAb titer values in the data are in inequality forms, the sign of inequality will be removed and then the values will be transformed.

Immunogenicity result for CT-P22 and CT-P23 are listed and summarized separately. The number and percentage of subject will be presented by treatment group and test at each scheduled time point for the safety population.

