11.3 Other Exploratory Analysis

Blood sampling for assessment of anti-influenza antibodies (Hemagglutination inhibition) will be collected on Day 1 (at pre-infusion) and Day 29 (\pm 5days) or EOS visit (if a subject is early terminated from the study) in Subgroup (PK) Cohort.

Genotypic analysis on Hemagglutinin (HA) and Neuraminidase (NA) genes, and phenotype characterization of potential escape variants with regard to CT-P27 will be assessed using the nasopharyngeal swab samples.

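### Under SAP 5.1 and 11.2, the only post-dose ADA/NAb result of a subject who leaves early is listed but not tabulated, so the tabulated percentage can fall below the incidence among sampled subjects

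*SAP*

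**What the plan says.** **Sampling.** Protocol 6.3: "Blood will be drawn at Day 1 (before study drug administration) and Day 110/EOS visit to evaluate the immunogenicity of CT-P27 components". Protocol 8.2.4 and the schedule of assessments give the same two occasions, with EOS as the alternative to Day 110. No other post-dose immunogenicity draw is scheduled.

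**Early leavers.** Footnote 22 to the schedule in protocol 4.1: "But if a subject is early terminated from the study, EOS visit will be done to assess safety parameters at any time". Protocol 4.3.4 says of subjects who withdraw that "they will be encouraged to return to the site for safety reasons to complete the assessments planned for EOS visit".

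**Summary rule.** SAP 5.1, on summarising the EOS visit: "the early termination cases are excluded from the summary for EOS visit, but will be presented in data listings". The sentence after it lets results into tables when they are needed to interpret the data, but only unscheduled results.

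**Immunogenicity table.** SAP 11.2: "The number and percentage of subject will be presented by treatment group and test at each scheduled time point for the safety population". It sets no exemption from SAP 5.1, no any-time post-baseline category and no denominator of its own.

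**Denominator and population.** SAP 5.1: "The denominator for all percentages will be the number of subjects within the treatment group for the population of interest, unless otherwise indicated". Protocol 8.4.3: "All safety and immunogenicity analyses will be based on the safety population". SAP 5.1 also calls for *Not done* and *Missing* categories in categorical summaries.

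The protocol's immunogenicity analysis (8.5.3) contains no exclusion of early-termination samples, and SAP section 13 does not list one among its changes.

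**The concern.** For most safety measures, dropping the early-termination EOS record costs one of several post-dose observations. For immunogenicity it costs the only one. The general rule in SAP 5.1 thus has an effect in SAP 11.2 that it has in few other places: a subject with a valid post-dose result looks in the table like a subject with none.

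Assessing immunogenicity is a stated exploratory objective, and Table 14.2.22 is where a reader will look for the ADA and NAb percentages. Protocol 2.4.1 describes past immunogenicity as very low. With few positives expected, one result that sits only in a listing can decide whether an arm shows none or some.

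**Working it through.** **Step 1: follow one subject through the rules.** A subject is dosed, leaves before Day 110, returns for the EOS visit and is bled.
- The sample is the subject's only post-dose ADA/NAb sample (protocol 6.3, 8.2.4).
- It belongs to an early-termination EOS visit, so SAP 5.1 removes it from the EOS summary.
- SAP 11.2 has no other row that could hold it.
- The result appears only in Listings 16.2.6.8.1 and 16.2.6.8.2.
- The subject received study drug, so stays in the safety population and, by default, in the denominator.

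**Step 2: effect on the percentage.** For one arm, let N be the safety population, c the subjects positive at Day 110, e the early leavers who are sampled and positive, and m the subjects with at least one post-baseline result (m ≤ N).
- Tabulated: c / N
- With early-termination samples counted, same denominator: (c + e) / N
- Difference: e / N
- Incidence among all sampled: (c + e) / m, which is at least (c + e) / N

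With N = 70 (the planned CT-P27 arm size, SAP 1.1) and assumed values of c and e:

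| c | e | tabulated | early-termination sample counted | difference (points) |
|---|---|---|---|---|
| 3 | 0 | 3/70 = 4.3% | 3/70 = 4.3% | 0 |
| 0 | 1 | 0/70 = 0% | 1/70 = 1.4% | 1.4 |
| 3 | 1 | 3/70 = 4.3% | 4/70 = 5.7% | 1.4 |
| 3 | 2 | 3/70 = 4.3% | 5/70 = 7.1% | 2.9 |

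For the placebo arm of 43, one such subject is 1/43 = 2.3 points.

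**Step 3: does the direction depend on the denominator?** Suppose the table used only subjects with a Day 110 result. Take 70 subjects, one of them a sampled early leaver, and 3 positives among the other 69. The table shows 3/69 = 4.35%. If the early leaver is positive, the figure among all sampled is 4/70 = 5.71%, which is higher. If negative, it is 3/70 = 4.29%, which is lower. The downward direction therefore belongs to the SAP's default denominator.

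**Step 4: can the documents supply the size?** The only figure near the question is the 10% dropout in SAP 5.2. It reproduces: 164/0.9 = 182.2, rounded up to 183; per arm 63/0.9 = 70 and 38/0.9 = 42.2, rounded up to 43; 70 + 70 + 43 = 183. But it inflates the number evaluable for the primary endpoint and is not a Day 110 termination rate. The same section also assumes that 90% of subjects are eligible and infected, yet divides by 0.9 only once, so it is unclear how much of the 10%, if any, is early termination. It gives no usable count here.

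**The case against.** The strongest reply has four parts.

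- **The effect is conditional.** A reader might infer that ADA incidence *is* understated. The text does not support that. A positive is lost from the table only if a subject leaves early, returns, is sampled and is positive. Attendance is only encouraged, and past immunogenicity was very low. This stands.
- **The direction rests on a default.** Excluding cases could mean removing the subjects from both numerator and denominator, and no table shell settles it. The *Missing* and *Not done* categories may show early leavers as having no Day 110 result rather than as negative. This stands as a limit. But *Missing* would then describe subjects whose post-dose result exists, so the information is still absent from the table.
- **Day 110 has a rationale.** It lies at about five half-lives, whereas an early EOS visit can fall at any time. Pooling the two mixes lengths of follow-up, and early negatives could dilute a combined rate. This is a reason to keep the Day 110 row unchanged and to label a second row. It does not justify having no second row.
- **Nothing is destroyed.** The results are listed, and the endpoint is exploratory and descriptive. True, and it limits the severity, but a listing does not change a tabulated percentage.

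Three further inferences are tempting and not supported. Applying the 10% dropout to each arm to count lost results fails for the reasons in Step 4, and would also assume that every early leaver is sampled. Selective loss, with ADA-positive subjects leaving because of reactions, is speculation: the documents do not link ADA to withdrawal. The HI antibody sample, also drawn at "or EOS visit (if a subject is early terminated from the study) in Subgroup (PK) Cohort", is a separate matter. SAP 11.3.1 defines the HI response as Day 29 against baseline, so an off-schedule sample is left out by that time point rather than by the EOS exclusion.

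**Conclusion.** The gap is real and follows from the text. One post-dose sample, a general exclusion of early-termination EOS data and a table by scheduled time point without exemption together keep available post-dose ADA/NAb results out of the immunogenicity summary. Under the default denominator the tabulated percentage can be at or below, never above, the incidence among all sampled subjects. The shift caused by the exclusion is e/N: zero if no sampled early leaver is positive, and 1.4 points for each one in an arm of 70.

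That figure is an assumed illustration. The actual size would need an ADA rate, an early-termination rate to Day 110 and the share of early leavers who are sampled, and the documents give none of them. The downward direction assumes that SAP 11.2 uses the default denominator. This is a modest reporting defect in an exploratory summary, worth correcting because the correction is simple and leaves the planned table intact.

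**What to change.** In SAP 11.2, exempt immunogenicity from the SAP 5.1 exclusion by adding one row for ADA and one for NAb to Table 14.2.22: *positive at any post-baseline sample (Day 110 or early-termination EOS)*.

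- State the denominator for that row as subjects with at least one post-baseline result, and print the number. Its percentage will also differ from the Day 110 row because of this denominator, so both counts should be visible.
- Keep the scheduled Day 110 row as it is.
- Add a footnote that the new row includes samples taken at varying times after dosing.

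The cost is a sentence in the SAP and the added row for each assay. The protocol already schedules the samples, so no new collection is needed. The small downside is the mixed sampling time, which the footnote discloses.
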